11.2 Calculation or derivation of safety variable(s)

Safety and tolerability will be assessed in terms of AEs, deaths, laboratory data and vital signs. These will be collected for all patients. Appropriate summaries of these data will be presented as described in [Section 12](#).

11.2.1 Other significant adverse events (OAE)

During the evaluation of the AE data, an AstraZeneca medically qualified expert will review the list of AEs that were not reported as SAEs and DAEs. Based on the expert's judgement, significant adverse events of particular clinical importance may, after consultation with the Global Patient Safety Physician, be considered OAEs and reported as such in the Clinical Study Report. A similar review of laboratory/vital signs/ECG data will be performed for identification of OAEs.

Examples of these are marked haematological and other laboratory abnormalities, and certain events that lead to intervention (other than those already classified as serious), dose reduction or significant additional treatment.

11.3 Calculation or derivation of patient reported outcome variables

Patient reported outcomes will be assessed based on the FACIT-Fatigue symptoms and the EORTC QLQ-C30 questionnaires. Further details are given in [Section 12.2.3](#) and full details will be provided in the statistical analysis plan.

11.4 Calculation or derivation of pharmacokinetic variables

The pharmacokinetic (PK) analysis of the plasma concentration data for olaparib will be performed at AstraZeneca R&D or by a CRO identified by AstraZeneca R&D. The actual sampling times will be used in the PK calculations. For each patient providing a complete set of PK samples, non-linear mixed effects modelling (NONMEM) will be used to estimate steady state C_{max} , AUC and C_{min} .

11.5 Calculation or derivation of pharmacodynamic variable(s) - not applicable

11.6 Calculation or derivation of pharmacogenetic variables

Any data summaries that will be reported in the main clinical study report will be detailed within the statistical analysis plan. Additional exploratory analyses or data summaries that may be produced outside of the main study report will be defined in an exploratory analysis plan, if appropriate.

11.7 Calculation or derivation of health economic variables –not applicable

12. STATISTICAL METHODS AND SAMPLE SIZE DETERMINATION

12.1 Description of analysis sets

A comprehensive statistical analysis plan (SAP) will be prepared before first subject in (FSI).

[Table 14](#) gives a summary of outcome variables and analysis populations.

12.1.1 Full analysis set

Intention to treat (ITT): The primary statistical analysis of the efficacy of olaparib will include all randomised patients and will compare the treatment groups on the basis of randomised

treatment, regardless of the treatment actually received. Patients who were randomised but did not subsequently go on to receive study treatment are included in the Full Analysis Set (FAS).

For the interim analysis two efficacy populations will be defined.

1. ITT population: This will include all randomised patients and will compare the treatment groups on the basis of randomised treatment, regardless of the treatment actually received. Note: it is anticipated that all patients will be randomised by the time of the interim analysis.
2. Mature cohort ITT population: This will include the first 900 randomised patients only and will compare the treatment groups on the basis of randomised treatment, regardless of the treatment actually received.

12.1.2 Safety analysis set

All patients who received at least one dose of randomised study treatment, olaparib or placebo, will be included in the safety analysis set. If a patient receives at least one dose of olaparib he/she will be summarised in the olaparib arm for safety summaries (e.g. olaparib arm will include patients randomised to olaparib who receive at least one dose of olaparib or placebo patients who receive at least one dose of olaparib in error at any time). If a patient randomised to olaparib receives only placebo treatment then he/she will be summarised as part of the placebo arm.

Table 14 Summary of Outcome Variables and Analysis Populations

Outcome Variable	Populations
Efficacy Data - Interim	
IDFS	FAS (ITT), Mature cohort ITT
Other efficacy variables	FAS (ITT)
Efficacy data- Final	
IDFS, OS, DDFS, incidence of contralateral breast cancers, new primary ovarian, new primary fallopian tube cancers and new primary peritoneal cancer and symptom/HRQoL endpoints	FAS (ITT)
Demography	FAS (ITT)
Pharmacokinetics data	PK
Safety Data	
Exposure	Safety
Adverse Events	Safety
Lab measurements	Safety
Vital Signs	Safety

12.1.3 PK Analysis set

PK data will be analysed according to treatment received. This population will comprise all randomised to olaparib patients who receive at least one dose of study treatment and have at least one PK sample collected.

12.2 Methods of statistical analysis

12.2.1 Analysis of primary endpoint

12.2.1.1 Primary analysis

The primary analysis of IDFS will occur when a minimum of 330 IDFS events have been observed (to provide at least 90% power to detect a hazard ratio of 0.7). Based on the event rate from the 10 November 2017 database, the number of IDFS events required to trigger the primary analysis is expected to be accrued by November 2020 (80% CI: March 2020 to September 2021). The maturity rate will be 18.3%, where maturity is defined as the number of events divided by the total number of randomised patients.

IDFS will be compared across two treatment arms using a log rank test stratified by the stratification factors at randomisation, and the corresponding p-value will be reported as the primary analysis result. In addition, IDFS will be analysed using a stratified Cox proportional hazard model stratified by the stratification factors at randomisation and using the Efron approach for handling ties. The point estimate of the treatment effect, i.e., the hazard ratio of IDFS (olaparib vs. placebo) will be obtained by maximizing the Cox partial likelihood function, which is the product of the partial likelihood of each stratum. The 95% confidence interval will be estimated using the profile likelihood approach.

A Kaplan-Meier plot of IDFS will be presented by treatment group. Summaries of the number and percentage of patients experiencing an IDFS event, and the type of event (recurrence or death) will be provided for each treatment.

The estimated 3 year IDFS will be summarised (using estimates from the KM curve) and presented by treatment group.

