12.2.2 Analysis of secondary endpoints

OS and DDFS

OS and DDFS will be analysed at the time of the IDFS analysis as per the multiple testing procedure (MTP) outlined in [Section 12.2.5](#) and will use the same methodology and model as described above for the primary analysis of IDFS.

If applicable, a sensitivity analysis will be performed for DDFS and OS using the same model as described above for IDFS but based on all randomised patients confirmed to have *gBRCA* mutations by the central test. This analysis is only required if the analysis population differs from the primary ITT population. Subgroup analyses will also be conducted for DDFS and OS based on the same subgroups described above for IDFS.

DDFS and OS will be analysed at the time of the primary analysis for IDFS (when 330 IDFS events are reported).

The final OS analysis will be conducted once the trial follow up is complete (i.e. 10 years from when the last patient is randomised, estimated 14 years from first patient randomised assuming recruitment of 5 years).

In addition another analysis will be performed half way between the primary IDFS analysis and the final overall survival analysis (estimated around 10 years from first patient randomised but timings will be driven by the primary IDFS analysis once known). At this time point both DDFS and OS will be analysed and some alpha will be reserved for formal hypothesis testing. IDFS may also be updated if more information is available but this would be considered a supportive update of the primary analysis and no alpha will be reserved for IDFS.

For details on alpha spend and how this will be allocated across the planned analyses see [Section 12.2.6](#).

Incidence of contralateral invasive breast cancer, contralateral non-invasive breast cancer, new primary ovarian cancer, new primary fallopian tube cancer and new primary peritoneal cancer

The actual number and percentage of patients with new contralateral breast cancers (invasive and non-invasive), new primary ovarian cancer, new primary fallopian tube cancer and new primary peritoneal cancers will be presented. In addition a table summarising all reported new cancers (i.e. not just breast, ovarian, fallopian tube or peritoneal cancers) will also be produced.

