12.2.6 Interim analysis

A superiority interim analysis of IDFS will occur when half the events needed for at least 90% power (165 events) have been observed from the first 50% of patients recruited (i.e. from first 900 patients) providing a cohort of patients with a similar level of maturity that is planned for the final analysis. Based on the database at time of amendment, the interim analysis is predicted to be October 2019 (80% CI: March 2019 to August 2020). The predictions will be tracked and monitored as more patients are enrolled in the study and additional data is added to the database. Two populations will be analysed at the interim analysis based on the analysis methods described in [Section 12.2.1](#) for IDFS

1. Primary: ITT population (all patients randomised, estimated 254 events [80% CI: 226 to 289])
2. Supportive: Mature cohort population (first 900 patients randomised, 165 events anticipated)

The inclusion of a mature cohort population at the interim is to provide confidence that any observed treatment effect from the interim ITT population is maintained with longer-term follow-up. It is anticipated, based on the assumed recruitment and event rate that the interim analysis will occur approximately 5.3 years after the first patient is randomised and that all patients will have been randomised. At the time of the interim analysis, median time at risk per patient is expected to be 27 months in the ITT set, and 34 months in the mature cohort. The critical HR value at the interim analysis is 0.701.

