Evidence of superiority for IDFS would only be determined at the interim if the results from both analysis populations provide evidence of a sustainable clinically relevant treatment effect for IDFS. More specifically, as a minimum the result in the ITT population would need to have met the statistical threshold defined below. Having met the statistical threshold in the ITT population, the result in the mature cohort (i.e. HR) would need to be of a similar magnitude such that the IDMC would consider it supportive of the ITT result and therefore have added confidence in the result in the ITT population. Statistical significance is not required for the mature cohort population. This analysis will be regarded as supportive, based on a cohort of patients with longer term follow-up, to aid interpretation of the result in the ITT population based on interim data. Other outcome measures such as 3 year IDFS rate will also be presented to aid the interpretation of the HRs (particularly in the case where the assumption of proportional hazards may not hold). KM plots will also be produced for IDFS.

The test mass alpha for IDFS (1 sided 2.5%) will be split between the final and the interim analysis using a bespoke spending function where a fixed significance level will be assigned at the interim and the remaining significance level assigned to the final analysis, taking account of correlation ([Stone 2010](#)). A 2-sided significance level of 0.005 will be assigned to the interim analysis so that a highly significant and clinically relevant result will need to be observed to declare superiority on IDFS. As an illustration, if 70% of the total required 330 IDFS events

have occurred in the ITT population at the interim then the observed HR would need to be < 0.7 for superiority to be declared. The HR in the mature cohort would need to be supportive of the ITT result. More detail around the criteria required for the mature cohort will be provided in the IDMC charter or SAP.

If the null hypothesis for IDFS is rejected at the interim for the ITT population then secondary endpoints (DDFS and OS) will be tested based on the MTP procedure outlined in [Section 12.2.5](#) using the significance levels provided in [Table 15](#). If IDFS is not significant at the interim, DDFS and OS will not be tested at the IDFS interim and the significance level allocated to the IDFS interim for DDFS and OS will not be allocated to later timepoints.

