Secondary endpoints will be assessed based on the ITT population. [Table 15](#) shows the different 2-sided significance levels that will be applied to the primary and secondary endpoints across the planned analyses as well as the total alpha spend for each endpoint. Note the significance level for the final analyses of each endpoint will be calculated using the relevant correlation based on the actual number of events for each analysis, the previous alpha spend and the total allocated alpha for that endpoint.

Table 15 Summary of 2-sided significance levels and total alpha spend across the endpoints and analyses

Endpoints	Interim analysis	Final IDFS analysis	DDFS and OS analysis	Final OS analysis	
Estimated timings from FSI**	5.3 years	6.5 years	10 years	14 years	
	Significance level	Significance level	Significance level	Significance level	Total alpha spend (2-sided)
IDFS	0.005	TBC*	N/A	N/A	5%
If IDFS is statistically significant and alpha is not recycled between secondary endpoints at the analysis					
DDFS	0.005	0.02	TBC*	N/A	4%
OS	0.002	0.003	0.004	TBC*	1%
If IDFS is statistically significant and alpha is recycled between secondary endpoints at the analysis					
DDFS	0.00625	0.025	TBC*	N/A	5%
OS	0.01	0.015	0.02	TBC*	5%

*TBC: to be calculated; significance level to be calculated once relevant correlation based on the actual number of events for each analysis is known taking account of previous alpha spend and total allocated alpha

**FSI: first subject in

The IDMC will review the data from the interim analysis. The boundaries defined by the interim p-values for efficacy will be used as guidelines by the IDMC along with all other relevant trial information, including the safety data, to decide if it is appropriate to make a recommendation other than that to continue the trial as planned.

At the time of the interim analysis for superiority, an assessment of futility will also be performed. This futility assessment will be based on the probability of eventually showing statistical significance for the primary endpoint when the final number of IDFS events (n=330) is reached ([Lachin 2005](#)). The determination of this probability will be conditional on the observed data in the ITT population at the time of the interim analysis for superiority and on the assumed hazard ratio for the alternative hypothesis (IDFS HR=0.7). If the probability is less than 0.1, the IDMC will consider the option of declaring futility.

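### At the interim IDFS analysis and the fixed DDFS and OS looks, the prescribed 95% interval can exclude 1 while the formal test is not significant

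*Protocol*

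**What the plan says.** Section 12.2.1.1 makes the stratified log-rank p-value the primary result and adds a stratified Cox hazard ratio, for which "The 95% confidence interval will be estimated using the profile likelihood approach". No other level is given for that interval.

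Two cross-references extend these methods:

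- Section 12.2.6, pointing to Section 12.2.1: "Two populations will be analysed at the interim analysis based on the analysis methods described in".
- Section 12.2.2, on OS and DDFS: they "will use the same methodology and model as described above for the primary analysis of IDFS".

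The levels that decide are in Section 12.2.6. For IDFS, "A 2-sided significance level of 0.005 will be assigned to the interim analysis". Table 15 gives the rest; the last figure in each row is the total two-sided percentage:

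- Without recycling: "DDFS 0.005 0.02 TBC* N/A 4" and "OS 0.002 0.003 0.004 TBC* 1".
- With recycling: "DDFS 0.00625 0.025 TBC* N/A 5" and "OS 0.01 0.015 0.02 TBC* 5".

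Section 12.2.5 also says that IDFS, DDFS and OS are each tested at two-sided 5% for descriptive purposes, with the multiple testing procedure added to control the overall error. The protocol does not say that the 95% interval belongs only to those descriptive tests, and it gives no interval matched to the Table 15 levels.

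**The concern.** A reader normally takes an interval that excludes 1 as agreeing with a significant test. That holds only when the interval level is 1 minus the test level. At the interim and at every fixed DDFS and OS look, the test level is well below 0.05, so the two can disagree.

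DDFS and OS are the key secondary endpoints intended for label claims. Suppose IDFS is significant and OS is then tested at 0.002 or 0.003 and fails. A reported 95% interval for OS that lies wholly below 1 would look like a survival benefit that the trial's own procedure did not establish.

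**Working it through.** **Inputs (protocol).** 1:1 allocation; 330 final IDFS events; 254 expected interim ITT events (80% CI 226 to 289); interim level 0.005; total IDFS alpha 5% two-sided; Table 15 levels.

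**Method.** SE of log HR = 2/√d for d events. A test at two-sided level a rejects in favour of olaparib when HR < exp(−2·z/√d), where z is the 1 − a/2 normal quantile. This approximates both the log-rank test and the profile-likelihood interval.

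**1. The plan's own figures.**
- Power with 330 events, HR 0.7 and two-sided 5%: 0.8997 (stated 90%).
- Interim critical HR with 254 events: exp(−2 × 2.807/√254) = 0.703 (stated 0.701, which corresponds to about 250 events).
- Final level from the bivariate normal with correlation √(254/330): 0.0496, critical HR 0.8056 (stated 0.805). With 226 or 289 interim events the final level is 0.0492 or 0.04995. A 95% interval is therefore adequate at the final IDFS analysis.

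**2. Interim IDFS.** The 95% interval excludes 1 below exp(−2 × 1.960/√254) = 0.782. The test rejects only below 0.703. Between the two they disagree. With 226 events this zone is 0.688 to 0.770, and with 289 it is 0.719 to 0.794.

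Example: HR 0.75, SE = 2/√254 = 0.1255.
- p = 0.022, not significant at 0.005
- 95%: exp(ln 0.75 ± 1.960 × 0.1255) = 0.586 to 0.959
- 99.5%: exp(ln 0.75 ± 2.807 × 0.1255) = 0.527 to 1.067

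Probability of landing in the zone in favour of olaparib: Φ(2.807 − m) − Φ(1.960 − m), with m = −ln(HR)·√254/2.

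| True HR | Probability |
|---|---|
| 0.70 | 30% |
| 0.75 | 33% |
| 0.80 | 28% |
| 1.00 | 2.25% |

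**3. Intervals that match each fixed look.**

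| Endpoint | Not recycled | Recycled |
|---|---|---|
| DDFS, interim / final IDFS analysis | 99.5% / 98% | 99.375% / 97.5% |
| OS, interim / final IDFS analysis / DDFS and OS analysis | 99.8% / 99.7% / 99.6% | 99% / 98.5% / 98% |

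With no treatment effect, the two-sided chance of disagreement at one look is 0.05 minus the level: 4.8% for OS at 0.002, 3.0% for DDFS at 0.02 and 2.5% for DDFS at 0.025.

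**4. Zone for OS.** The protocol gives no death counts, so these are assumptions.

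| Assumed deaths | OS at 0.002 | OS at 0.003 |
|---|---|---|
| 100 | 0.539 to 0.676 | 0.552 to 0.676 |
| 150 | 0.604 to 0.726 | 0.616 to 0.726 |
| 200 | 0.646 to 0.758 | 0.657 to 0.758 |

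**5. Zone for DDFS at 0.02 (z = 2.326).** No event count is given here either. Every DDFS event is also an IDFS event, so the count cannot exceed the IDFS count. Assuming 200, 250 or 300 events, the zone runs from exp(−2 × 2.326/√d) to exp(−2 × 1.960/√d): 0.720 to 0.758, 0.745 to 0.780, or 0.764 to 0.797.

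**The case against.** The strongest reply has four parts.

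- **The interval decides nothing.** Decisions rest on the log-rank p-value against Table 15. This is correct. A reader might infer that the 95% interval inflates type I error; the protocol does not support that.
- **Nobody outside the IDMC sees a failed interim.** Section 12.3 keeps interim reports in closed session, and the recommendation carries no outcome information. The IDMC also has the 0.005 boundary and the critical HR. If IDFS is not significant at the interim, Section 12.2.6 bars DDFS and OS testing there. This stands. The 28% to 33% figures measure how often the two readings would differ before the IDMC, not how often the public would be misled.
- **The 95% level has a purpose.** It matches the descriptive 5% tests in Section 12.2.5. This explains the choice, but the protocol does not tie the interval to those tests, so each endpoint has two readings and one unlabelled interval.
- **Interval levels are SAP detail.** Section 12.2.6 defers interim details to the SAP and IDMC charter, and the cross-references may have been meant to carry only the test and the model. The SAP was not available here and may settle this. But the protocol names 95% and then extends its methods to these looks, so the level is stated, not simply left open.

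A further tempting reading is that, when a boundary is crossed early, the 95% interval understates uncertainty. That does not follow. A 95% interval claims 95% confidence whatever level the test used. The matched interval is 43% wider on the log scale (2.807/1.960 = 1.43), but that ratio is not a loss of coverage.

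**Conclusion.** The point holds as a matter of reporting and interpretation. At the interim IDFS analysis and the fixed DDFS and OS looks, the stated 95% interval can exclude 1 when the formal test does not reject. The exposure that matters is in published DDFS and OS results after IDFS is significant, above all OS at 0.002 or 0.003. With 150 assumed deaths, any OS hazard ratio from about 0.60 (at 0.002) or 0.62 (at 0.003) up to 0.73 would show the conflict.

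The final IDFS analysis is not affected (level about 0.0496). The last DDFS and OS levels are still to be calculated, so no mismatch can be sized there. The sizes rest on the normal approximation, on 254 interim IDFS events, and on assumed DDFS and OS event counts. The conclusion also rests on reading the cross-references in Sections 12.2.2 and 12.2.6 as carrying the interval level along with the model.

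**What to change.** State that each hazard ratio tested under the multiple testing procedure is reported with an interval at 1 minus the two-sided level used at that look: 99.5% for interim IDFS, and the Table 15 level after any recycling for DDFS and OS, including the last looks once their levels are calculated. Label any 95% interval shown beside it as nominal and tied to the descriptive 5% tests of Section 12.2.5.

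This takes a sentence in the protocol or SAP and a change to the table shells. Design, sample size, alpha allocation and conduct stay as they are. The downside is wider intervals that look less favourable, and two intervals per estimate where both are shown.

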12.2.1.2 Sensitivity analysis

If applicable, an analysis will be performed for IDFS using the same model as described above but based on all randomised patients confirmed to have *gBRCA* mutations by the central test. This analysis is only required if the analysis population differs from the primary ITT population.

Any patients mis-stratified in the randomisation system (i.e. incorrect details are entered at the time of randomisation) will be included in the primary stratified log rank test and Cox proportional hazard model using the baseline data collected from the randomisation system (Registration and Randomisation System). If > 5% of randomised patients are incorrectly stratified (i.e., randomisation system data does not match baseline data), then a sensitivity analysis will be performed for IDFS based on the (correct) baseline data collected in the eCRF. If the results of ER and PgR status from the local and central labs differ in >5% of randomised

patients, a sensitivity analyses will also be performed based on ER and/or PgR positive/HER2 negative and TNBC subsets as defined by the central laboratory testing.

The assumption of proportionality will be assessed. Proportionality will be tested firstly by producing plots of complementary log-log (event times) versus log (time) and, if these raise concerns, a time dependent covariate would be fitted to assess the extent to which this represents random variation. Note that in the presence of non-proportionality, the HR will be interpreted as an average HR over the observed extent of follow-up.

As patients will be randomised, imbalances in demographic factors between the treatment groups are not anticipated. However if any imbalances should occur, these additional demographic variables may be fitted into the stratified Cox model. The HR and associated confidence interval would be presented.

